6.4 Subgroup analysis

For Part B and Part C, subgroup analyses based on age group (18 to 55 years, 56 to 85 years, 18 to 64 years, and 65 to 85 years), comorbidities which are relevant for COVID-19, i.e., obesity (BMI <30 kg/m² and BMI ≥ 30 kg/m²), and diabetes mellitus (yes and no) will be performed for immunogenicity endpoints and primary safety endpoints.

6.5 Other summaries and analyses

The conversion rule for days to month and days to year, the analysis visit, the definition of baseline and the computation of trial day are as defined in [Section 3.4](#).

6.5.1 Baseline and demographic characteristics

6.5.1.1 Demographic characteristics

Demographic characteristics, including age (years) at screening and age group (18 to 55 years, 56 to 85 years, 18 to 64 years, and 65 to 85 years), sex, childbearing potential (yes or no), ethnicity, race, country, height(cm), body weight(kg), Body Mass Index (BMI [kg/m²])

Underweight (below 18.5), Normal weight (18.5 to 24.9), Over weight (25 to 29.9), Obese (30 and above)), diabetes mellitus (yes or no), baseline SARS-CoV-2 infection status (Positive or Negative), and Time from the second dose of BNT162b2 (received prior to the trial) to the first trial vaccination (days) will be summarized for each cohort and trial part based on Safety Set, Immunogenicity Analysis Set, and all randomized subjects for Part C. For Part C, type of test performed, when the last SARS-CoV-2 infection prior to the IMP dose was diagnosed (time between prior SARS-CoV-2 infection and trial randomization), whether infection with SARS-CoV-2 Omicron variant confirmed, number of prior COVID-19 RNA vaccines and time from the last dose of COVID-19 RNA vaccination (received prior to the trial) to trial randomization will be presented by Cohort. Summary for the control group subjects from the Phase III trial BNT162-02 / C4591001 will also be included.

6.5.1.2 Medical history

Each reported medical history term will be mapped to a system organ class (SOC) and preferred term (PT) according to MedDRA. The number and percentage of subjects having at least 1 diagnosis, overall and at each SOC and PT level, will be summarized for the Safety Set and all randomized subjects for Part C by Cohort and trial part.

6.5.2 Trial conducts and subject disposition

6.5.2.1 Subject disposition

The numbers and percentages of subjects on Screened Set who received vaccinations (IMP Doses 1, 2 and 3, as applicable for each cohort), who completed treatment and completed the trial will be tabulated by cohort. In addition, the number and percentage of subjects who discontinued treatment early and/or withdrew from the trial early along with the primary reasons for treatment discontinuation, withdrawn after last IMP dose and before 1 month post- last IMP dose visit, withdrawn after 1 month post last IMP dose visit, will be tabulated by cohort. The primary reasons for trial discontinuation will be those as specified in the database. Subjects in Cohort 2 who received two IMP doses and in Cohort 6 who received three IMP doses will be considered as treatment completer.

Subjects excluded from each analysis set will also be summarized separately along with the reasons for exclusion by cohort and trial part. Summary for the control group subjects from the Phase III trial BNT162-02 / C4591001 will also be included.

6.5.2.2 Protocol deviation

The number and percentage of subjects in the Screened Set with Important protocol deviation (IPD) will be presented by cohort and trial parts, for each protocol deviation category/sub-category. Also, a listing of all protocol deviations (PDs) will be presented.

6.5.2.3 Blood samples for assay

The number and percentage of subjects' blood sample drawn for immunogenicity will be tabulated for the Safety set and all randomized subjects for Part C by cohort and trial Part. A listing of subjects providing blood samples within and outside of the protocol-specified time frames will be provided. Summary for the control group subjects from the Phase III trial BNT162-02 / C4591001 will also be included.

6.5.2.4 E-diaries

E-diary transmission will be summarized by cohort and trial part using the Safety Set. A listing of subjects who were vaccinated and completed e-diaries after each dose will be provided.

6.5.3 IMP exposure

For each dose, the number and percentage of subjects receiving each trial intervention will be tabulated for each cohort and trial part.

6.5.4 Prior/Concomitant medications and concomitant procedures

Prior and Concomitant medications (CM) will be summarized, separately, by Anatomic Therapeutic Chemical (ATC) classification level 4 and preferred name for the Safety Set and all randomized subjects for Part C by cohort and trial part. The number and percentage of subjects receiving each medication after Dose 1 will be tabulated by cohort and trial part.

Concomitant medications administered due to local reactions and systemic events during time interval Day 1 to 7 days post each dose will be summarized. Bar chart with the number and percentage of subjects with any CM for local reactions and systemic events.

Concomitant procedures (including non-drug therapies) will be listed only.

6.6 Other safety analyses

Local reaction, systemic event, AE, and SAE summaries and analyses are described under Primary Endpoints in [Section 6.1.1](#).

6.6.1 Laboratory assessments

Safety laboratory parameters including hematology, clinical chemistry analysis, and urinalysis will be summarized at screening using descriptive summary statistics for each parameter by cohort and trial part for safety set.

Abnormal and clinically significant, abnormal and not clinically significant, and normal laboratory values will be summarized for each parameter at baseline by cohort and trial part.

Laboratory results will be listed along with the reference ranges and values below or above the reference ranges will be flagged.

6.6.2 Vital signs and physical examinations

Vital sign parameters to be summarized using descriptive statistics for heart rate, systolic blood pressure and diastolic blood pressure. Absolute values and change from baseline for oral temperature will be summarized by cohort and visit for each trial part.

Absolute values and change from baseline for each ECG parameters will be summarized by cohort, and visit for each trial part. Baseline is the last non-missing measurement or sample collected prior to first IMP injection.

Abnormal clinically significant, abnormal not clinically significant, and normal values of ECG assessment and heart rate will be summarized by visit, Cohort and trial part. Number

of subjects with missing measurements for post dose visits will be computed as number of subjects who received the specific dose minus the number of subjects with non-missing values at each visit.

Physical examinations including body weight will be performed and clinically significant abnormalities will be summarized by cohort and trial part. At a minimum, assessments of cardiovascular, respiratory, gastrointestinal, and neurological systems will be performed.

7 ANALYSES TIMING

7.1 Interim analyses and summaries

No formal interim analysis will be performed. However, the safety and immunogenicity analysis with data up to 1 month post dose for Part A (Cohort 1, 3, 4 and 5), 1 month post Dose 2 for Part A (Cohort 2 and 6) will be performed.

7.2 Safety Review Committee

This trial will use an SRC. The SRC will at least comprise a sponsor medical representative, the Medical Monitor, an independent medical physician, an independent cardiologist, a statistician, coordinating investigator, a sponsor-independent investigator, and on an *ad hoc* basis, a representative for the respective trial site depending on the trial subject in question.

Safety reviews of the data will be conducted by the SRC approximately every 4 weeks and on an *ad hoc* basis. The SRC will review all safety data, including AESIs, and SAEs, as well as laboratory data and other relevant safety data.

After all subjects enrolled into Part A, Part B and Part C have completed their 1 month follow-up visit, the SRC members will continue to receive safety data (related AEs, AESIs, SAEs) on a monthly basis, but further SRC meetings will occur approximately every 6 months unless triggered earlier by SRC member requests or if suspected unexpected serious adverse reactions (SUSARs)/AESIs are reported.

All outputs required and data cut off requirements will be documented prior to each SRC. More details can be found in latest SRC charter.

8 CHANGES IN STATISTICAL ANALYSIS FROM PROTOCOL

8.1 Additional analysis sets for safety and immunogenicity analysis

In [Table 8](#) of [Section 4](#), All Randomized Subjects was added for demographic and other baseline data analysis in Part C. Immunogenicity Analysis Per Protocol Set and All-available Immunogenicity Set (mITT) were added for additional immunogenicity analysis in Part B and C immunogenicity.

8.2 Changes in interim analysis

the safety and immunogenicity analysis with data up to 1 month post dose for Part A (Cohort 1, 3, 4 and 5), 1 month post Dose 2 for Part A (Cohort 2 and 6) will be performed. The primary immunogenicity analysis for all Part B cohorts and for Part C Cohorts 7 and 8 will be performed in the final analysis for clinical study report.

8.3 Withdrawal of primary objectives to demonstrate the non-inferiority of immune response against VOC (B.1.1.7 and B.1.617.2) after two doses of multivalent vaccine BNT162b2 (B.1.1.7 + B.1.617.2) in terms of GMT and SR for COVID-19 vaccine-naïve subjects in Part B Cohort 6

In COVID-19 vaccine naïve individuals (recruited into cohort B6), the original primary immunogenicity objectives were to demonstrate the non-inferiority of immune response against Variants of Concern (B.1.1.7 and B.1.617.2) after two doses of multivalent vaccine BNT162b2 (B.1.1.7 + B.1.617.2) to the immune response after two doses of original BNT162b2 in subjects without evidence of infection from the Phase I/ II/ III trial BNT162-02/ C4591001 in terms of geometric mean titer (GMT) and seroresponse rate (SR).

By the time the cohort had been fully recruited in August 2022, approximately 75% participants recruited into cohort B6 – required to be without known history of SARS-CoV-2 infection, self-reported at the screening visit according to the exclusion criteria - retrospectively turned out to be seropositive for SARS-CoV-2 by planned N-binding antibody assessment at baseline. The cohort hence was COVID-19 vaccine-naive, but not SARS-CoV-2-naïve as originally foreseen.

In BNT162-17 protocol version v7.0, new primary and secondary immunogenicity objectives for COVID-19 vaccine-naïve subjects in Part B were introduced aiming to support FDA authorization of a single-dose primary regimen of the 2023/2024 season variant-adapted BNT162b2 vaccine targeting XBB.1.5 in previously unvaccinated individuals with and without previous SARS-CoV-2 infections. The new primary immunogenicity objectives were thus to demonstrate the non-inferiority of immune response against reference strain after one dose of multivalent vaccine BNT162b2 (B.1.1.7 + B.1.617.2) in COVID-19 vaccine-naïve subjects with evidence of prior infection (cohort B6 of BNT162-17) to the immune response after two doses of original BNT162b2 in subjects without evidence of infection from the Phase I/ II/ III trial BNT162-02/ C4591001 in terms of GMT and SR.

The original objectives in cohorts B1 and B4, the new primary immunogenicity objective in cohort B6, the primary safety objectives and all secondary objectives in cohort B6 will be analysed according to the clinical trial protocol (CTP).

However, since the population recruited into cohort B6 (unvaccinated but not SARS-CoV-2 naïve) did not reflect the originally foreseen population for this cohort, it was decided that the data analysis for the original primary immunogenicity endpoints for cohort B6 would not be performed according to the CTP. Concretely that entails the following:

-
1. While Variants of Concern (VOC) and reference strain Virus Neutralization Tests (VNTs) will be determined for all samples taken in BNT162-17 cohort B6, the data will not be used for the primary endpoint. The data will be used to address secondary and exploratory endpoints only.
 2. The control cohort from the pivotal study BNT162-02, in which two doses of BNT162b2 were assessed in previously unvaccinated individuals, will not be picked and no data will be generated.
 3. An amendment to the CTP was no longer possible because the study had been closed in one of the four countries it was performed in and global end of trial was achieved on 04 October 2023. The above approach will therefore be described in the statistical analysis plan (SAP) and clinical study report (CSR).

10 APPENDICES

Appendix 1. List of abbreviations

Abbreviation	Term
AE	Adverse event
AESI	Adverse event of special interest
BNT162b2 (B.1.1.529)	Monovalent vaccine specific for SARS-CoV-2 Omicron subvariant BA.1, i.e., B.1.1.529.1
BNT162b2 (B.1.1.7)	Monovalent vaccine specific for SARS-CoV-2 Alpha variant
BNT162b2 (B.1.617.2)	Monovalent vaccine specific for SARS-CoV-2 Delta variant
CI	Confidence interval
CD	Cluster of differentiation, e.g., CD4, CD8, glycoproteins that serves as a co-receptor for T-cell receptors
COVID-19	Coronavirus disease 2019
CMI	Cell-mediated immune
CRF	Case report form
e-diary	Electronic diary
EDC	Electronic Data Capture (system)
GMC	Geometric mean concentration
GMFR	Geometric mean fold rise
GMR	Geometric mean ratio
GMT	Geometric mean titer
IgG	Immunoglobulin G
IMP	Investigational Medicinal Product
LLOQ	Lower limit of quantitation
MedDRA	Medical Dictionary for Regulatory Activities
MH	Medical history
N/A	Not applicable
NAAT	Nucleic acid amplification-based test
NT	Neutralizing titer
PT	Preferred term
RBD	Receptor binding domain
RNA	Ribonucleic acid
S	Spike protein
S1	Spike protein S1 subunit
SAE	Serious adverse event
SAP	Statistical Analysis Plan
SARS-CoV-2	Severe Acute Respiratory Syndrome Coronavirus 2
SOC	System organ class
SP1	Spike protein pool 1
SP2	Spike protein pool 2
SR	Seroresponse
SRC	Safety Review Committee
TEAE	Treatment-emergent adverse event
VOC	Variant of concern

Appendix 2. Subject selection for primary and secondary immunogenicity analysis in Part B

To perform the primary immunogenicity analyses specified in [Section 6.1.2.5](#) and [6.1.2.6](#) and the secondary immunogenicity analyses specified in [Section 6.2.2.7](#), [6.2.2.8](#), [6.2.2.9](#), and [6.2.2.10](#), subjects in trial BNT162-17 and the control group subjects in Phase III trial BNT162 02 / C4591001 were selected with the following criteria:

- COVID-19 vaccine-naïve subjects with evidence of prior SARS-CoV-2 infection in Part B Cohort 6 who had positive test results (n-capsid and NAAT test) at baseline; did not have key protocol deviations that lead to exclusion from immunogenicity analysis; immunogenicity samples at 3-week post Dose 1 were collected within grace period window (16 to 26 days from Dose 1); and had sufficient volume of serum samples were eligible for the analysis.

For comparison between subjects in Cohort B1 without evidence of infection and subjects in Cohort B6 with prior infection, an equivalent number of subjects were selected from B6 positive group randomly to match number of B1 negative subjects. These subjects are randomly selected to support the Variants Neutralizing Titers analysis.

- COVID-19 vaccine-naïve subjects without evidence of SARS-CoV-2 infection in Part B Cohort 6 who had negative n-capsid test result at baseline and 1-month post Dose 2; **negative local and central NAAT test result from baseline to 1-month post Dose 2; no COVID-19 infection AE events**; did not have key protocol deviations that lead to exclusion from immunogenicity analysis; immunogenicity samples at 1-month post Dose 2 were collected within grace period window (19 to 39 days from Dose 2); and had sufficient volume of serum samples were eligible for the analysis.
- COVID-19 vaccine-experienced subjects with one booster dose of BNT162b2 (B.1.1.7 + B1.617.2) without evidence of SARS-CoV-2 infection in Part B Cohort 1 who had negative n-capsid test result at baseline and 1-month post Dose 1; did not have key protocol deviations that lead to exclusion from immunogenicity analysis; immunogenicity samples at 1-month post Dose 1 were collected within grace period window (19 to 39 days from Dose 1); and had sufficient volume of serum samples were eligible for the analysis.
- Subjects without evidence of SARS-CoV-2 infection in Pfizer Phase III trial BNT162-02 / C4591001
 - had sufficient blood volume at baseline and 1-month post dose 1 (total volume >1000 unit)
 - had no evidence of infection up to 1-month post Dose 2
 - enrolled in Phase 3 part of the trial and randomized to BNT162b2 30 mcg group and received 2 doses of BNT162b2 30 mcg
 - HIV negative and not in multiple trials
 - did not have important PDs
 - did not violate inclusion criteria
 - had 1MPD2 (V3) blood draw within 28-42 days after Dose 2

- were not enrolled in BNT162-17 trial.

After applying above conditions, there were ~20,000 subjects eligible. Subjects were selected randomly with matching age and sex with each of subjects in Part B Cohort 6 of BNT162b2-17 (~276 total) using SAS Proc Surveyselect procedure.

To perform the primary analyses specified in [Section 6.1.2.1](#), [6.1.2.2](#), [6.1.2.3](#), and [6.1.2.4](#), subjects in trial BNT162-17 and the control group subjects in Phase III trial BNT162 02 / C4591001 were selected with the following criteria:

- BNT162b2 vaccine-experienced subjects with one booster dose of BNT162b2 (B.1.1.7 + B1.617.2) in Part B Cohort 1 and with one booster dose of BNT162b2 (B1.617.2) in Part B Cohort 4 who had valid samples at baseline and 1-month post Dose 1 were eligible for the analysis.
- Subjects in Pfizer Phase III trial BNT162 02 / C4591001
 - were randomized originally to BNT162b2 Phase 2/3 (30 mcg)
 - had two doses at vaccination 1 and 2 as randomized
 - were not enrolled in BNT162-17 trial
 - sample volume at baseline (V1) and 1 month post 2nd dose (V3) are >500 unit
 - enrolled in phase 3 study, HIV negative, and not in multiple trials
 - not selected for analysis specified in [Section 6.1.2.5](#) and [6.1.2.6](#) and the secondary immunogenicity analyses in [Section 6.2.2.7](#), [6.2.2.8](#), [6.2.2.9](#).

After applying above conditions, there were ~20,000 subjects from Pfizer Phase III trial BNT162 02 / C4591001_eligible. Subjects were selected randomly with matching age and sex with each of eligible subjects in Part B Cohort 1 and Cohort 4 of BNT162b2-17 (~700 total) using SAS Proc Surveyselect procedure.

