4 ANALYSIS SETS (POPULATIONS FOR ANALYSIS)

Data for all subjects will be assessed to determine if they meet the criteria for inclusion in each analysis set. All analysis sets will be assessed and documented prior to releasing the database for each cohort.

For all trial parts, analyses of safety endpoints will be performed using the Safety Set. Subjects will be summarized for safety analysis according to the vaccine group they actually received. For Part C, demographic and baseline characteristics, medical history,

and prior medications will be tabulated for all randomized subjects as well. Analyses of primary, secondary and exploratory immunogenicity endpoints will be performed using Immunogenicity Analysis Set, Immunogenicity Analysis Per Protocol Set, and/or All-available Immunogenicity Set (mITT) as specified in Sections 6.1.2, 6.2, and 6.3. For mITT, subjects will be summarized according to the vaccine group to which they were randomized/assigned. The analyses of reactogenicity endpoints (i.e., local reactions and systemic events) will be based on Reactogenicity Set. The definitions of each analysis set are specified below in Table 8.

Table 8. Analysis set

Analysis set	Description
Screened Set	All subjects who signed informed consent.
All Randomized Subjects	All subjects who were randomized to Cohort 7, 8, 9 in Part C
Safety Set	All subjects who received at least one dose of IMP.
Reactogenicity Set	All subjects included in the Safety Set with any e-diary data reported after IMP injection.
Immunogenicity Analysis Set	All eligible randomized/assigned subjects who receive the trial intervention to which they are randomized or assigned, have a valid and determinate immunogenicity result from the blood sample collected within an appropriate window ^a , and have no other important protocol deviations that can confound immunogenicity data ^{c,d} .
Immunogenicity Analysis Per Protocol Set	All eligible randomized/assigned subjects who receive the trial intervention to which they are randomized or assigned, have a valid and determinate immunogenicity result from the blood sample collected within per protocol window ^b , and have no other important protocol deviations that can confound immunogenicity data ^{c,d} .
All-available Immunogenicity Set (mITT)	All randomized/assigned subjects who receive the trial intervention and have a valid and determinate immunogenicity result after the trial intervention.

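### External controls for the Cohort 1 and 4 primary tests are selected without the deviation, inclusion-violation and draw-day criteria required of the Cohort 6 controls, and no text says that the test arms' analysis-set filter covers them

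*SAP*

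**What the plan says.** Appendix 2 of the SAP contains two lists of criteria for controls taken from the same Phase III trial.

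- **Controls for the Cohort 6 comparison (SAP 6.1.2.5 and 6.1.2.6).** Among other conditions, a control "did not have important PDs", "did not violate inclusion criteria" and "had 1MPD2 (V3) blood draw within 28-42 days after Dose 2".
- **Controls for the Cohort 1 and 4 comparisons (SAP 6.1.2.1 to 6.1.2.4).** A control must have been randomized to the 30 µg arm, "had two doses at vaccination 1 and 2 as randomized", "enrolled in phase 3 study, HIV negative, and not in multiple trials", not have entered BNT162-17 and not already be in use as a Cohort 6 control. On samples the list says only "sample volume at baseline (V1) and 1 month post 2nd dose (V3) are >500 unit". It has no deviation criterion, no inclusion-violation criterion and no range of days.

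On the test side, Appendix 2 takes Cohort 1 and 4 subjects "who had valid samples at baseline and 1-month post Dose 1 were eligible for the analysis". Protocol 9.4.3.1 and 9.4.3.2 then run the primary GMT and seroresponse tests on the Immunogenicity Analysis Set. SAP Section 4 (Table 8) requires members of that set to "have no other important protocol deviations that can confound immunogenicity data" and to have a sample inside the grace-period window of SAP Table 7, which is day 19 to day 39 for the 1-month visit.

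**The concern.** These are confirmatory tests against a non-randomized external group, so the two sides should pass the same quality filter. The SAP treats the criteria as material: Table 7 classes an out-of-window sample as affecting immunogenicity, and as an important deviation where it supports a primary endpoint. The notes to Table 8 give examples of important deviations, including medication that may alter the immune response and errors that may reduce vaccine potency. Such subjects leave the test arm, but nothing in the text removes them from the control arm.

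If controls that would fail have lower titers, keeping them lowers the reference GMT and the reference seroresponse rate, and both tests become easier to pass. Matching on age and sex does not address this. The listed sensitivity analyses for Cohorts 1 and 4 (unadjusted estimates, and a subset without infection) apply no deviation or draw-day filter to controls, so they would not reveal the asymmetry.

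**Working it through.** **1. The criteria side by side**

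| Criterion | Cohort 6 controls | Cohort 1/4 controls | Cohort 1/4 test arms |
|---|---|---|---|
| Important deviations excluded | yes | not stated | yes (Table 8) |
| Inclusion violations excluded | yes | not stated | Table 8 requires eligible subjects |
| 1-month draw window | days 28 to 42 | nominal visit V3 only | days 19 to 39 (Table 7) |
| Dosing as randomized or assigned | yes | yes | yes |

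**2. Does the Immunogenicity Analysis Set already cover the controls?** Table 8 describes subjects randomized or assigned in this trial who received its intervention, which the Phase III controls did not. The Cohort 6 control window also differs from Table 7. A Cohort 6 control drawn on days 40 to 42 is accepted by Appendix 2 but would be out of window under Table 7. So Table 7 is not simply carried over to controls, and the window for Cohort 1 and 4 controls cannot be deduced. SAP 6.1.2 asks for results at 1 month after the second dose and gives no days.

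**3. The plan's own power figure.** Inputs from Protocol 9.2.2 and Table 11: GMR 0.8, margin 0.67, SD 0.70 on the natural-log scale, 300 evaluable (taken as per group), one-sided 0.025.

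- SE = 0.70 × √(2/300) = 0.0572
- Power = Φ(ln(0.8/0.67)/SE − 1.96) = Φ(0.1773/0.0572 − 1.96) = 87.3%; the plan states 87%.
- SDs of 0.65 and 0.75 give 91.6% and 82.5%; the plan states 92% and 82%.

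The sample-size figures reproduce. The gap lies in control selection alone.

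**4. Illustration of the possible effect.** Let a share f of controls fail the missing criteria and have titers r times those of the rest. Neither f nor r is in the documents. The GMR is multiplied by r^(−f). With the SD held fixed, the one-sided error at a true GMR of 0.67 is Φ(−f·ln r/SE − 1.96).

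| f | r | GMR multiplied by | One-sided error |
|---|---|---|---|
| 2% | 0.9 | 1.002 | 2.7% |
| 5% | 0.7 | 1.018 | 5.0% |
| 5% | 0.5 | 1.035 | 8.8% |
| 10% | 0.7 | 1.036 | 9.1% |
| 10% | 0.5 | 1.072 | 22.8% |

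Worked line: for f = 5% and r = 0.7, the shift is 0.05 × 0.3567 = 0.0178; 0.0178/0.0572 = 0.312; Φ(0.312 − 1.96) = 5.0%.

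If failing controls instead had higher titers, the sign reverses. With f = 5% and r = 1/0.7, Φ(−0.312 − 1.96) is about 1.2%, which is conservative.

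These errors are for a single GMT comparison exactly at the margin. Cohort 1 success needs both variants, and each cohort also needs seroresponse. No effect on seroresponse was computed.

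**The case against.** The strongest reply is that Appendix 2 is only a selection step and the analysis set is applied afterwards to both arms. Neither bullet for these comparisons mentions deviations, and the test-arm filter itself comes from Table 8. Protocol 9.4.3.1 and 9.4.3.2 define the whole comparison on the Immunogenicity Analysis Set. SAP 6.5.1.1 summarizes demographics on that set and includes the controls, SAP 6.5.2.1 includes them in the account of exclusions from analysis sets, and SAP 6.5.2.3 includes them in the account of sample collection. This stands as evidence that a filter on controls may be intended. It does not supply the filter: these are reporting sections, and no sentence says that Table 8 applies to controls or which day window they must meet.

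Three stronger readings are tempting, and the documents do not support them.

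- **That there is no 1-month requirement at all.** A nominal V3 sample is required by the quoted criterion and by SAP 6.1.2. Only the range of days is missing.
- **That dosing errors go unfiltered.** The list requires "had two doses at vaccination 1 and 2 as randomized", which covers at least part of this.
- **That the tests are shown to be biased towards success, with error of 9% to 23%.** Those values need 5% to 10% of controls to fail and every one of them to have half the titer. The documents give no failure rate and no direction. Some deviations could raise titers, and this control list has no infection exclusion, so infection-boosted controls would make the GMT test conservative. Both lists also report roughly 20,000 eligible subjects although the Cohort 6 list excludes more, which hints that few would fail. The counts are rounded and the lists differ in other criteria too, so this is only a hint.

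**Conclusion.** The point holds as a gap in specification with a possible one-sided filter; it is not a demonstrated bias. The Cohort 1 and 4 controls are chosen by an explicit list that lacks three criteria required of the Cohort 6 controls, and the analysis set that filters the test arms is not stated to include them. Across the assumed inputs with lower titers among failing controls, the one-sided error for one GMT comparison runs from 2.7% to about 23%. The upper end depends on severe inputs, and the error falls below 2.5% if failing controls have higher titers. The planned power is not in question. Because the comparison is non-randomized and confirmatory, and the planned sensitivity analyses would not show the problem, the text should be changed.

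**What to change.** State in Appendix 2 and in Table 8 that controls for SAP 6.1.2.1 to 6.1.2.4 must meet the same important-deviation and inclusion-violation exclusions as the other groups, and give a prespecified V3 day window for them. If that window differs from Table 7, say why.

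Exclude already selected controls that fail from the primary analysis, report how many and for which reason, and repeat the analysis with all selected controls as a sensitivity analysis.

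Replacing failing controls should be optional. The pool is large (about 20,000 for about 700 places, or 29 to 1), but Appendix 2 describes the selection as already made and SAP 8.3 dates the end of trial to 04 October 2023, so replacement may need new assays.

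The cost is SAP wording and a small loss of controls. Starting from 300 per arm, dropping 5% leaves 285 controls: SE = 0.70 × √(1/300 + 1/285) = 0.0579, and power goes from 87.3% to about 86.5%. Dropping 10% leaves 270: SE = 0.0587 and power is about 85.5%. If the 700 places split evenly, each cohort has about 350 controls, and a 10% loss leaves 315, still above 300.
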